3.2.3 Replication Trial Design

[figure not shown]
This replication trial is a cluster-randomized, NIH-defined Phase III pragmatic trial. The study statistician, in partnership with data analysts at MGB, will generate and implement the randomization scheme, with oversight by the Principal Investigators. All the study sites will be at MGH for this trial; we have received approval from leadership at MGH primary care practices and Digital Health eCare teams to conduct this trial. For study evaluation, data regarding patients' medical history, disease control, medication use, and healthcare utilization will be obtained from EHR data or administrative claims data. The administrative claims data used for evaluation in this study will come directly from MGB in HIPAA-limited datasets through their risk-bearing contracts, as applicable.

We plan to randomize primary care providers at MGH to one of the 2 most promising treatment arms identified in the adaptive randomized trial conducted at Atrius Health or usual care. We expect to randomize approximately 200 providers. Providers randomized to one of the 2 selected treatment arms will receive an EHR tool to guide their care of eligible patients. If the adaptive trial does not demonstrate the superiority of any EHR tools over usual care, we will select the two statistically most promising of the arms for this parallel group trial. We will randomize providers based on provider demographic characteristics, patient case-mix factors, and baseline rates of high-risk medication prescribing measured in EHR data.

[figure not shown]
Providers will be eligible if they prescribed a benzodiazepine, sedative hypnotic, or two distinct anticholinergics to at least one older adult in the 180 days prior to randomization. Providers will receive these EHR tools for their patients who meet the following criteria: 1) older adults (aged 65 years or more), and 2) who have been prescribed at least 90 pills of benzodiazepine or sedative hypnotic or have been prescribed at least one active orders of at least 90 pills of two different anticholinergics in the last 180 days. Follow-up will last 12 months. These patients will also be included in the analyses. The type and timing of EHR tool that the providers receive for these patients will vary based on their assigned intervention arm.

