3.7 Data sources

We will use EHR data to implement the EHR tools, identify study subjects, track study progress, and evaluate the effect of the interventions. We will also use administrative claims data to evaluate tertiary outcomes among the subgroup of patients with claims data.

The Atrius data warehouses reside in an Oracle environment and consist of the Clarity and Payer databases. The Clarity database is a relational database that contains clinical and financial information from the Epic Suite of products; including the electronic medical record system, the appointment scheduling system, the patient accounting system, and the master

patient index (Identity). The various tables within the Clarity database are refreshed on a daily, weekly or monthly basis.

For the claims data, the Medicare claims data are being provided by the funder, the National Institute on Aging (NIA), through their partnership with Acumen and the established MedRIC (<https://www.medric.info/data-enclave/data-pages/data>). In order to obtain claims data from the funder, we will provide them with Medicare Beneficiary Identifier (MBI) for linked patients in our study. We are executing all appropriate data use agreements with the NIA and Acumen to receive these data. The claims data will be available for linked patients in our study.

At MGB, we will extract clinical information from the electronic medical record system via the Epic Enterprise Data Warehouse (EDW) or the Mass General Brigham Research Patient Data Registry (RPDR). Accessing the EDW in particular is necessary in order to adequately identify and link all eligible patients seen by the enrolled providers in our study and measure outcomes, which is not possible using other sources.

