In Stage 2 and the replication trial, tertiary outcomes will include the extent to which medications are filled and consumed by patients, as measured within the subgroup of patients with claims data. In specific, these outcomes will be conducted among the large subgroup of patients funded by Medicare, including pharmacy claims via the secure MedRIC data enclave. In particular, we will measure the quantity of high-risk medication dispensed, defined by number of milligram equivalents of high-risk medications filled by patients, in follow-up, using pharmacy claims data. Other tertiary outcomes will include the occurrence of clinically-significant adverse drug events, including but not limited to, sedation or cognitive impairment, and all-cause hospitalizations and falls or fractures, measured in administrative claims data. These clinical outcomes will be evaluated using validated and CMS-driven ICD-10-CM diagnosis and procedure-based algorithms applied to these patients' medical and pharmacy administrative claims data. Because the sensitivity of clinical outcomes in EHR systems is known to be low (e.g., because patients may seek subsequent care at other healthcare systems), using routinely-collected data from insurers overcomes this limitation.³⁰ We will also evaluate implementation of the intervention using structured deidentified data from the EHR about use of the EHR system, which will help inform how to scale the interventions (see Data to be collected form).

At the conclusion of the trial, a brief optional survey will be administered electronically to providers who were included in the trial (see “Provider outreach email” and “Provider survey” in attachments). The purpose of the survey is to understand providers' satisfaction with the decision support and what modifications they would recommend in the future. These findings will be used to help understand implementation of the decision support and potential for scalability to other settings. The surveys will be prepared in MGB REDCap and delivered by secure email from the Atrius Site PI and will be completely optional. The survey will collect

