For the secondary outcome of cumulative medication prescribing, will use an identity link function and normally distributed errors within the generalized linear models. For tertiary adverse clinical outcomes and resource utilization outcomes, we will use a log link function and binary distributed errors within the overall multivariable models. These models generate the estimated relative risks (RRs) with robust standard errors and are considered to be particularly appropriate when outcomes are common (e.g., incidences of $\geq 10\%$). For these outcomes from claims data, we will follow patients whose providers are randomized to the study from the time

of randomization until they are censored due to loss of continuous enrollment in their health plan or leaving Atrius Health. Due to the nature of the randomization, we do not anticipate any systematic differences in the amount of follow-up time per arm but will account for any imbalances using inverse probability censoring weights.

Because this is a randomized trial, our primary analyses are planned as unadjusted; however, if there are strong patient-level predictors of the outcomes not balanced by stratified randomization, we will adjust for these in the primary analyses. Given the nature of the data and how the outcomes are being measured, there should not be missing values. However, should there be sufficient missing data (e.g., >10%), we will use multiple imputation.³¹

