7.3.3 Baseline descriptive analyses

We will report the means and frequencies of pre-randomization variables separately for intervention and control subjects. Comparisons of these values will be performed using t-tests and chi square tests and their non-parametric analogs, as appropriate. The outcomes will be evaluated using intention-to-treat principles among all randomized patients.

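### Claims-based tertiary outcomes are censored when a patient leaves Atrius, although the linked Medicare claims can still observe that patient

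*Combined protocol and SAP*

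**What the plan says.** Section 7.3.2 (Analysis of secondary endpoints) follows patients for outcomes from claims data from randomisation until they are "censored due to loss of continuous enrollment in their health plan or leaving Atrius Health". It expects no systematic difference between arms in length of follow-up and says that any imbalance will be handled with inverse probability censoring weights. It names no covariates or model for the weights, and no analysis that follows leavers in the claims.

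Other sections bear on that rule:

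- **Source of the claims.** Section 3.7 says the Medicare claims come from the funder through an outside data enclave, and that "we will provide them with Medicare Beneficiary Identifier (MBI) for linked patients in our study".
- **Population.** Section 6.2 says of the tertiary outcomes that "these outcomes will be conducted among the large subgroup of patients funded by Medicare, including pharmacy claims via the secure MedRIC data enclave".
- **Reason for using claims.** Section 6.2 says EHR sensitivity for clinical outcomes is low "because patients may seek subsequent care at other healthcare systems", and that insurer data solve this.
- **Analysis principle.** Section 7.3.3 says: "The outcomes will be evaluated using intention-to-treat principles among all randomized patients".
- **Replication trial.** Section 3.2.3 says its claims "will come directly from MGB in HIPAA-limited datasets through their risk-bearing contracts", whereas section 6.2 puts Stage 2 and the replication trial together under the Medicare linkage.

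**The concern.** Leaving a delivery network is not the same as losing insurance. For a patient linked to Medicare by beneficiary identifier, falls, fractures, hospitalisations and emergency visits remain visible after the move. The rule stops counting them anyway. It does so at an event that occurs after randomisation, in an open-label trial, so it cannot be assumed unrelated to arm.

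The claims outcomes also have a particular job here. Under section 6.2, a patient with no further order during follow-up counts as a success on the primary outcome, and the secondary outcome counts prescribing by Atrius providers. A patient who leaves and obtains the drug elsewhere could look like a success on both. Dispensed quantity from pharmacy claims is the one listed outcome that could show the drug had merely moved. If it falls under the same censoring rule, that check is lost for exactly those patients.

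**Working it through.** **Reading the sections together.** Section 7.3.2 gives two grounds for censoring joined by *or*. Loss of enrolment is already one of them, so the second ground has an effect only on patients who have left Atrius but are still enrolled. For those linked under section 3.7, neither the data holder (the funder) nor the key (the beneficiary identifier) depends on Atrius. Their later outcomes are observable and are set aside. That follows from the text without any assumed rate.

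**Scale.** The documents give no leaving rate, event rate or power figure for these outcomes, so there is no figure to reproduce. The two illustrations below use assumed inputs.

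*Illustration 1: a clinical event.* Assume 8 months of follow-up (section 3.6), constant hazard, a 10% event risk for those who stay, leaving times uniform over follow-up, 5% leaving in usual care and 10% in the tool arms, hazard doubled after leaving, and no other tool effect. The cumulative hazard for a stayer is −ln(0.90) = 0.10536.

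- Mean risk of a leaver over the whole 8 months: 1 − 0.81 × (0.11111/0.10536) = 0.1458.
- Mean risk of a leaver up to leaving: 1 − 0.10/0.10536 = 0.0509.
- Full follow-up: tool arms 0.90 × 0.10 + 0.10 × 0.1458 = 0.1046; usual care 0.95 × 0.10 + 0.05 × 0.1458 = 0.1023. RR = 1.022.
- Censored, no weights: tool arms 0.90 × 0.10 + 0.10 × 0.0509 = 0.0951; usual care 0.95 × 0.10 + 0.05 × 0.0509 = 0.0975. RR = 0.975.
- Censored, weights by arm only: RR = 1.00, because before leaving the hazard is the same in both arms.
- Share of events discarded: 9.1% in the tool arms, 4.6% in usual care.

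Other assumed settings, all with 5% leaving in usual care (ranges cover stayer risks of 10% and 20%):

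| Leaving, tool arms | Hazard multiplier after leaving | RR, full follow-up | RR, censored, unweighted | RR, arm-only weights |
|---|---|---|---|---|
| 5% | 1 to 3 | 1.00 | 1.00 | 1.00 |
| 8% | 1.5 to 2 | 1.006 to 1.013 | 0.985 | 1.00 |
| 10% | 1.5 to 2 | 1.011 to 1.022 | 0.975 | 1.00 |
| 15% | 3 | 1.074 to 1.085 | 0.950 to 0.951 | 1.00 |

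*Illustration 2: dispensed quantity, if the rule covers it.* Assume 5% leave in usual care and 8% in the tool arms, all at the midpoint. Usual-care quantity is 1.

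- No tool effect, unweighted: usual care 0.95 + 0.05 × 0.5 = 0.975; tool arms 0.92 + 0.08 × 0.5 = 0.960. Arm-level weights return both to 1.000, so the apparent 1.5-point difference disappears.
- Tool effect present: quantity is 0.90 in the tool arms, except that the extra 3% who leave fill at 1.0 throughout. The true difference is 1 − (0.97 × 0.90 + 0.03 × 1.0) = 0.097. Unweighted: 0.975 − (0.92 × 0.90 + 0.05 × 0.45 + 0.03 × 0.5) = 0.975 − 0.8655 = 0.1095. Weighted: the first half is 0.5 × 0.903 = 0.4515 and the second half 0.5 × 0.90 = 0.45, so the difference is 1 − 0.9015 = 0.0985.
- The error is 1.25 points unweighted and 0.15 points weighted. The weights remove 1.10/1.25 = 88% of it.

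Both illustrations show that weights repair unequal follow-up time. What they leave is the part due to leavers differing from stayers in ways the weight model does not contain.

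**The case against.** The strongest reply is that the plan already has a remedy, and on simple assumptions it works well: arm-level weights remove all of the bias in one case above and most of it in the other. That stands, and it is why the size given here is small. What it does not answer is why outcomes should be modelled by weighting when they can be observed, or which covariates the weights will use.

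A second reply is that claims still serve their purpose under the rule, since they capture a fall treated elsewhere while the patient belongs to Atrius, and that stopping when the patient leaves the setting of the intervention is a defensible estimand. This is fair as far as it goes, but section 7.3.3 promises intention to treat among all randomised patients, and the plan offers no other estimand.

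A reader might go further in four ways that the documents do not support:

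- *That the tools drive patients away and the rule therefore favours the tools.* Nothing in the plan shows differential leaving, and section 7.3.2 expects none. It is possible, but only assumed.
- *That dispensed quantity is certainly affected.* In section 7.3.2 the follow-up sentence comes after the adverse clinical and resource-use outcomes. Fills are covered only on a broad reading, although no other follow-up rule is given for them.
- *That claims always continue after leaving.* This is clear only for the Medicare-linked patients. Section 8.3 also describes Atrius itself disclosing claims, and the replication trial's contract claims may end when the patient leaves.
- *That the replication trial must use the Medicare linkage.* Section 8.3 describes sharing the beneficiary identifier only for Atrius data, so that would be more than a change of wording. The amendment log also records a supplemental analysis plan for that trial. No separate document of that name is available here, and it may define censoring.

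**Conclusion.** The point holds for the Medicare-linked patients of the Atrius trial. As written, section 7.3.2 discards outcomes that the chosen data source can still show, contrary to the plan's own reason for using claims and to its intention-to-treat statement.

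The consequence is probably small. Bias arises only if leaving, or what follows it, differs by arm; with equal leaving and equal risk afterwards, every RR above is 1.00 and the loss is one of information. With 8% to 10% leaving in the tool arms and a hazard 1.5 to 2 times higher after leaving, the weighted analysis misses an RR of 1.006 to 1.022. The extreme assumed case (15% leaving, hazard tripled) misses 1.074 to 1.085. All these rates are assumptions. Section 2 lists the outcomes as tertiary or exploratory, and the primary and secondary results are not touched by this rule.

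For the replication trial the point is narrower. Leaving Atrius has no meaning there, and sections 3.2.3 and 6.2 name different claims sources. The source decides whether leavers remain visible.

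**What to change.** 1. **Section 7.3.2, Atrius trial.** For patients linked to Medicare claims, make the main analysis follow each patient from randomisation to the earliest of end of follow-up, death or loss of Medicare enrolment, in the arm of the provider at randomisation. State that this covers dispensed quantity as well as the clinical and utilisation outcomes.
2. **Sensitivity analysis.** Keep censoring at leaving Atrius, and specify the weight model: its covariates, and whether weights are fitted by arm. Report the number leaving, by arm.
3. **Replication trial.** Reconcile section 3.2.3 with section 6.2 on the claims source, and state a censoring rule that matches the source actually used.

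For Atrius the cost is SAP wording, since the claims are already requested by beneficiary identifier. The downside is slight dilution from care outside the network, which belongs to the intention-to-treat effect. The replication trial needs a decision on its source before its rule can be written.

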7.3.3 Baseline descriptive analyses

We will report the means and frequencies of pre-randomization variables separately for intervention and control subjects. Comparisons of these values will be performed using t-tests and chi square tests and their non-parametric analogs, as appropriate. The outcomes will be evaluated using intention-to-treat principles among all randomized patients.

7.3.4 Subgroup analyses

In subgroup analyses, we will explore whether there were any modifiers of the effects of the EHR tools. For example, we will explore if certain types of providers (e.g., by specialty) were more likely to respond to the EHR tools or if there were observable differences in patients who were less likely to receive inappropriate medications, such as gender or race/ethnicity.

7.3.5 Exploratory analyses

In secondary analyses, we will control for potential confounders which will be measured using EHR data from structured fields and administrative claims data. These variables will include provider characteristics (such as specialty, age, and gender), patient characteristics (such as major comorbidities, race/ethnicity, and age), and practice characteristics (such as practice size).

8. Ethical and regulatory requirements

8.1 Ethical conduct

General oversight of the project by the principal investigators (Drs. [name] and [name]) will occur throughout the study period, including regular contact with practice managers and clinical leadership at each health center to obtain ongoing feedback. In addition, this protocol will undergo Institutional Review Board (IRB) evaluation by a centralized IRB for this multi-site clinical trial. Study data will be accessible at all times for the principal investigators (Drs. [name] and [name]) and co-investigators to review, if applicable. The principal investigators will review study conduct (e.g., protocol deviations) on a monthly basis. The principal investigators will also ensure that all protocol deviations for the trials are reported to the NIH and the IRB according to the applicable regulatory requirements.

We believe that the risks to participation for both sets of subjects (i.e. providers and patients) are no more than minimal for several reasons.

First, the intervention aims to emphasize guideline-recommended information for providers to assist in their decision-making when caring for older patients. Second, all treatment decisions will ultimately be made by licensed health care providers. Finally, the intervention is specifically provider-focused and delivered in an electronic health record system using information already available to providers. We believe there is no more than minimal risk involved to the provider subjects, as the providers will simply be “nudged” to alter their behaviors towards guideline recommended care, as opposed to being forced to do so. All medical decisions are ultimately made by the provider. This trial will not interfere with the ordinary workings of the outpatient centers.

There is a small risk associated with altering medication prescribing behaviors, including allergic reactions or other adverse medication effects; however, these risks are no more than are encountered during routine clinical care and are less than patients would

otherwise encounter if there were to receive the high-risk medications whose use the intervention seeks to reduce. In addition, these risks will be minimized in our protocol as we are relying on the provider to prescribe as they see best for their patient; the prescribing changes in the EHR tools are simply suggestions, not rigid rules for the providers. In addition, as described above, in the unexpected situation in which the EHR tools lead to worse prescribing decisions, we will discontinue those arms at the end of Stage 1.

The primary risk to patients will be privacy of health information. We will minimize the risk to privacy by taking appropriate steps to limit access to data to study investigators. Clinical data on the care for patients will be retrieved from the electronic medical records and insurer administrative claims. The data extracts obtained from the electronic medical record are continuously used by Atrius clinical operations staff for quality assessment and improvement, and undergo routine, rigorous peer-review by experienced data analysts to ensure accuracy and completeness. Drs. [name] and [name] will work with the research project staff to ensure the accuracy of these data throughout the study period. For the purpose of conducting analyses of the study outcomes, this will involve creating scrambled patient and provider identifiers and sharing only limited Protected Health Information (PHI) with investigators for the purposes of analysis. The link between the identifiers and the medical record number will remain at Atrius Health in a password protected file. All team members have received appropriate training in data privacy.

8.2 Informed consent

We will enroll provider-subjects based on their being employed by Atrius Health (adaptive trial) or Mass General Brigham (replication trial) as an outpatient primary care provider. As with other minimal-risk, quality improvement studies we have performed that involve electronic alerts to providers, formal informed consent will not be sought. First, the nature of this quality improvement intervention involves testing EHR decision support directly

for providers (using information already available to them and a similar infrastructure they use in the course of regular clinical care). Second, the ability to understand the true effect of the intervention as it is delivered in the real world would be difficult to ascertain if true informed consent was sought. Third, obtaining true informed consent would predictably reduce the number of patients participating in the study, especially those from unrepresented populations, and therefore undermine the generalizability of the study results, a foundational aspect of pragmatic clinical trial principles. Fourth, this approach has been approved by clinical leadership at the health organization. In our prior work at these institutions, we have received a waiver of informed consent from the IRBs of these organizations for similar interventions. We also request a HIPAA waiver of patient authorization to access the administrative claims and EHR data necessary for outcome evaluation, as doing so would be impractical and infeasible to conduct the study.

While providers and patients will not be consented into the study, an organization-wide announcement will be circulated across Atrius to inform providers of the launch of an intervention leveraging clinical decision support tools to support improved prescribing for older adults.

